NON-INTERVENTIONAL (NI) STUDY PROTOCOL

PASS information

A Dana Hilization Study to Evaluate Ladicators of			
A Drug Utilization Study to Evaluate Indicators of			
Adherence to the Risk Minimization Measures for			
Ritlecitinib Using Electronic Healthcare Data in Denmark,			
France, and Sweden			
B7981102			
1.0			
01 March 2024			
To be registered before the start of data collection			
Ritlecitinib			
ATC code L04AF08			
Litfulo [®]			
ELI/1/22/1755/001 ELI/1/22/1755/002 ELI/1/22/1755/002			
EU/1/23/1755/001, EU/1/23/1755/002, EU/1/23/1755/003			
EMEA/H/C/006025			
Pfizer Europe MA EEIG			
[name]			
[name]			
Belgium			
No			
Research Question:			
To what extent do routinely collected data indicate health			
care professional's (HCP) adherence to the			
recommendations for the use of ritlecitinib described in the			
Summary of Product Characteristics (SmPC), HCP guide,			
and Patient Card?			
The study objectives are to:			
1. Evaluate, to the extent measurable in the available			
routinely collected data, indicators of HCP's adherence to			
the risk minimization measures (RMMs) in accordance with			
the ritlecitinib SmPC, HCP guide, and Patient Card,			
specifically:			

PFIZER CONFIDENTIAL

	 Performing laboratory tests of lymphocyte count, platelet count, hepatitis B/C, and tuberculosis (TB) screening prior to initiation of ritlecitinib treatment Performing laboratory tests of lymphocyte count and platelet count at week 4 (± 2 weeks) from initiation of ritlecitinib treatment Avoiding live attenuated vaccines shortly before and during treatment with ritlecitinib No use during pregnancy No use in patients aged < 12 years No use during serious infections Describe the characteristics of patients before initiation of ritlecitinib treatment, in terms of: Risk factors for thromboembolic events (including deep vein thrombosis (DVT), pulmonary embolism (PE), and arterial thrombosis) Risk factors for malignancy Risk factors for cardiovascular disease (CVD) 	

2. LIST OF ABBREVIATIONS

Abbreviation	Definition
AA	alopecia areata
AE	adverse event
ATC	Anatomical Therapeutic Chemical
ATE	arterial thromboembolism
aRMMs	additional Risk Minimization Measures
AT	alopecia totalis
ATE	arterial thromboembolism
AU	alopecia universalis
BCG	Bacille Calmette-Guérin
CABG	coronary artery bypass graft
CCAM	Classification commune des actes médicaux
CESREES	Comité Ethique et Scientifique pour les Recherches, les Etudes et les
	Evaluations dans le domaine de la Santé
CI(s)	confidence interval(s)
CIOMS	Council for International Organizations of Medical Sciences
CIP	Code Identifiant de Présentation
CNIL	Commission Nationale de l'Informatique et des Libertés
CPR	Central Personal Registry
CVD	cardiovascular disease
DNPR	Danish National Prescription Registry
DVT	deep vein thrombosis
EC	ethics committee
EMA	European Medicines Agency
ENCePP	European Network of Centres for Pharmacoepidemiology and
	Pharmacovigilance
EU	European Union
GPP	Good Pharmacoepidemiology Practices
GVP	Good Pharmacovigilance Practices
HCP	healthcare professional
HMA	Heads of Medicines Agencies
ICD	International Statistical Classification of Diseases
ICD-10	International Classification of Disease, Tenth Revision
ICD-11	International Classification of Disease, Eleventh Revision
IRB(s)	Institutional Review Board(s)
ISPE	International Society for Pharmacoepidemiology
JAK	Janus Kinase
KVÅ	Klassifikation av vårdåtgärder
MAH	Marketing Authorization Holder
MMR	measles, mumps, rubella
NI	non-interventional
NIS	non-interventional study

PFIZER CONFIDENTIAL

Abbreviation	Definition
NMSC	nonmelanoma skin cancer
NOMESCO	Nordic Medico-Statistical Committee
NPU	Nomenclature, Properties and Units
PAS	Post-authorization studies
PASS	Post-authorization safety study
PCI	Percutaneous intervention
PE	pulmonary embolism
PY(s)	person-year(s)
RMMs	Risk Minimization Measures
RWD	real world data
SAP	Statistical Analysis Plan
SmPC	Summary of Product Characteristics
SNDS	Système National des Données de Santé
TB	tuberculosis
UCD	Unité Commune de Dispensation
US	United States
VTE	venous thromboembolism
WHO	World Health Organization

4. ABSTRACT

Title A Drug Utilization Study to Evaluate Indicators of Adherence to the Risk Minimization Measures for Ritlecitinib Using Electronic Healthcare Data in Denmark, France, and Sweden

Protocol B7981102; Version 1.0; 01 March 2024

Main author: [name], Aarhus University

Rationale and background Alopecia areata (AA) is an autoimmune disease that has an underlying immuno-inflammatory pathogenesis and is characterized by nonscarring hair loss ranging from small patches to complete scalp, face, and/or body hair loss. Ritlecitinib was authorized by the European Medicines Agency (EMA), on 15 September 2023, for the treatment of severe AA in adults and adolescents 12 years of age and older. To mitigate the risks associated with ritlecitinib use, required routine risk minimization measures (RMMs), including the Summary of Product Characteristics (SmPC) and package leaflet, are being employed. This noninterventional study (NIS) is designated as a post-authorization safety study (PASS) and is a commitment to the EMA.

Research question and objectives

Research Question: To what extent do routinely collected data indicate health care professional's (HCP) adherence to the recommendations for the use of ritlecitinib described in the Summary of Product Characteristics (SmPC), HCP guide, and Patient Card?

The study objectives are to:

- 1. Evaluate, to the extent measurable in the available routinely collected data, indicators of HCP's adherence to the risk minimization measures (RMMs) in accordance with the ritlecitinib SmPC, HCP guide, and Patient Card, specifically:
 - Performing laboratory tests of lymphocyte count, platelet count, hepatitis B/C, and tuberculosis (TB) screening prior to initiation of ritlecitinib treatment
 - Performing laboratory tests of lymphocyte count and platelet count at week 4 (\pm 2 weeks) from initiation of ritlecitinib treatment
 - Avoiding live attenuated vaccines shortly before and during treatment with ritlecitinib
 - No use during pregnancy
 - No use in patients aged < 12 years
 - No use during serious infections
- 2. Describe the characteristics of patients before initiation of ritlecitinib treatment, in terms of:
 - Risk factors for thromboembolic events (including deep vein thrombosis (DVT), pulmonary embolism (PE), and arterial thrombosis)
 - Risk factors for malignancy
 - Risk factors for cardiovascular disease (CVD)

Study design This is a descriptive drug utilization study using secondary data from healthcare databases in Denmark, France, and Sweden. These countries have universal healthcare.

Population The study population will include patients identified in each data source with a record of treatment with ritlecitinib from 15 September 2023 through 14 September 2028. Patients will not be required to have a recorded diagnosis of AA.

Variables The study will collect relevant data including patient demographics, comorbidities, prescription medications, vaccine administrations, and laboratory testing prior to the initiation of ritlecitinib and during treatment with ritlecitinib to address the study objectives.

Data sources This study will utilize routinely collected electronic healthcare data from national or regional population-based electronic healthcare registers in Denmark, France, and Sweden.

Study size All patients initiating ritlecitinib during the study period will be included.

Data analysis Data will be analysed in each country separately using a common protocol, database-specific definitions of the study variables, and a common analysis strategy. The main measures will be proportions of ritlecitinib users with a given indicator of RMM adherence.

Milestones Data collection will start in September 2027 and end in September 2030. Results will be summarized in a September 2028 interim report and a March 2031 final report.

5. AMENDMENTS AND UPDATES

None.

6. MILESTONES

Milestone	Planned date ^a	Comments
Registration in the EU	August 2027	Prior to initiating data collection.
PAS register		
Draft protocol submission	March 2024	Within 6 months from approval of ritlecitinib in
		the European Union (EU).
Start of data collection ^b	September 2027	Within 4 years from approval of ritlecitinib in
		the EU.
End of data collection ^c	September 2030	Within 2 years after the end of study period,
		considering the lag in data availability in the
		respective data sources.
Interim Report	September 2028	Interim study report planned for submission
		within 5 years of approval of ritlecitinib in the
		EU, considering the lag in data availability in
		the respective data sources.
Final study report	March 2031	Final study report is planned for submission
		within 6 months from the end of data collection.

a EU approval 15 September 2023.

b Defined as the date from which data extraction starts.

c Defined as the date from which the analytical dataset is completely available, i.e., clean and coded data from all participating countries/databases.

7. RATIONALE AND BACKGROUND

Alopecia areata (AA) is an autoimmune disease that has an underlying immuno-inflammatory pathogenesis and is characterized by nonscarring hair loss ranging from small patches to complete scalp, face, and/or body hair loss. AA may present as: limited patchy hair loss (patchy alopecia areata), complete loss of hair on the scalp (alopecia totalis [AT]), or complete loss of hair on the scalp and the body (alopecia universalis [AU]). The affected skin usually does not have signs of inflammation.

Both males and females of all ages and races can be affected. AA is the second most common cause of hair loss, affecting approximately 147 million individuals worldwide, with a lifetime risk of all subtypes of approximately 2% (1, 2). Incidence rates of AA range from 20 to 200 per 100,000 person-years [PY(s)], and the global lifetime prevalence worldwide is estimated at 2% (2-8). A meta-analysis including articles published up to 01 September, 2018 estimated the overall pooled incidence proportion of AA in Europe as 4.92% (95% confidence interval [CI] 2.41-8.25%), and the pooled prevalence as 0.58% (95% CI 0.49-0.66%) (9). AA is associated with inflammatory diseases including asthma, allergic rhinitis, atopic dermatitis, and autoimmune diseases such as thyroiditis and vitiligo (10). The natural history and prognosis of AA are unpredictable and can be marked by remission, progression, or persistence (11, 12).

Ritlecitinib was authorized by the European Medicines Agency (EMA), on 15 September 2023, for the treatment of severe alopecia areata in adults and adolescents 12 years of age and older (13). Ritlecitinib is flagged by the Danish authorities as a medication being subject to heightened monitoring (14).

To mitigate the risks associated with ritlecitinib use, required routine risk minimization measures (RMMs), including the Summary of Product Characteristics (SmPC) and package leaflet, are being employed. In addition to the routine RMMs, Pfizer has agreed to implement additional risk minimization measures (aRMMs) following ritlecitinib approval in the EU, including an educational program intended to enhance the communication of the risks and risk minimization practices to healthcare professionals (HCPs) via an "HCP Guide" and to patients via a "Patient Card". The patient card is a tool that reminds the patient of certain action(s) to take for risk minimization or aims to ensure that information regarding the patient's current treatment with the medicinal product and its risks is held by the patient at all times and used as a communication aid with healthcare professionals. The overall objective of the agreed aRMMs is to provide appropriate tools designed to enhance the awareness and knowledge of HCPs and patients about the safety risks and to ensure the optimal use of ritlecitinib.

An evaluation of the database-measurable indicators of adherence of HCPs with the RMMs will help understand whether the program objectives have been met and if further amendments to the program may be needed. Therefore, Pfizer aims to evaluate indicators of adherence to the routine and additional RMMs for ritlecitinib in three EU countries: Denmark, France, and Sweden.

This noninterventional study (NIS) is designated as a post-authorization safety study (PASS) and is a commitment to the EMA.

8. RESEARCH QUESTION AND OBJECTIVES

8.1. Research Question

The research question is: to what extent do routinely collected data indicate health care professional's (HCP) adherence to the recommendations for the use of ritlecitinib described in the Summary of Product Characteristics (SmPC), HCP guide, and Patient Card?

8.2. Study Objectives

The study objectives are to:

- 1. Evaluate, to the extent measurable in the available routinely collected data, indicators of HCP's adherence to the risk minimization measures (RMMs) in accordance with the ritlecitinib SmPC, HCP guide, and Patient Card, specifically:
 - Performing laboratory tests of lymphocyte count, platelet count, hepatitis B/C, and tuberculosis (TB) screening prior to initiation of ritlecitinib treatment
 - Performing laboratory tests of lymphocyte count and platelet count at week 4 (± 2 weeks) from initiation of ritlecitinib treatment
 - Avoiding live attenuated vaccines shortly before and during treatment with ritlecitinib
 - No use during pregnancy
 - No use in patients aged < 12 years
 - No use during serious infections
- 2. Describe the characteristics of patients before initiation of ritlecitinib treatment, in terms of:
 - Risk factors for thromboembolic events (including deep vein thrombosis (DVT), pulmonary embolism (PE), and arterial thrombosis)
 - Risk factors for malignancy
 - Risk factors for cardiovascular disease (CVD)

9. RESEARCH METHODS

9.1. Study Design

This will be a descriptive drug utilization study using data from healthcare databases in Denmark, France, and Sweden.

9.1.1. Study Population and Study Period

The study population will include patients identified in each data source with a record of treatment with ritlecitinib during the study period. The study period will be 5 years following product launch: from 15 September 2023 through 14 September 2028.

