9.1.2. Index Date

The date of the first dispensing or administration of ritlecitinib during the study period will be the index date.

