9.2.1. Inclusion Criteria

Patients must meet all of the following inclusion criteria to be eligible for inclusion in the study:

- 1. Have at least one dispensing of ritlecitinib during the study period
- 2. Have at least 12 months of continuous history in a participating data source before the index date

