9.3.1. Exposure

The date of the first dispensing of ritlecitinib during the study period will be the index date. The exposure will continue until the end of a 90-day grace period following the estimated discontinuation of the index treatment. Duration of each dispensing will be computed based on days supplied, estimated based on assumed daily dose, package size, and number of packages in each dispensing. Only the first continuous treatment episode will be considered in this study.

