9.7. Data Analysis

This is a descriptive study and the data will be analysed and results presented separately by country. Counts and proportions for categorical variables and mean and median with ranges for continuous variables will be calculated to address the study objectives, as below. All proportions will be reported with 95% CIs.

Data sources vary in collection of laboratory test and vaccine information (data on both laboratory tests and their results are available in Denmark; data on performed laboratory tests, but not results, are available in France; laboratory data are not available in Sweden). Data on vaccines are not available in Sweden.

Counts and proportions will be calculated for:

- 1. Patients with evidence of having performed the following laboratory tests and screenings within 3 months before index date:
 - Lymphocyte count
 - Platelet count
 - Screening for TB
 - Screening for viral hepatitis B and C
- 2. Patients with evidence of having performed the following laboratory tests at week 4 (\pm 2 weeks) after index date:
 - Lymphocyte count
 - Platelet count

- 3. Patients with evidence of having received live attenuated vaccines within 4 weeks before index date
- 4. Patients with evidence of having received live attenuated vaccines during treatment with ritlecitinib
- 5. Females in whom pregnancy, as recorded in the available data sources, overlaps with ritlecitinib use
- 6. Patients aged <12 years on the index date
- 7. Patients with a serious infection before index date
- 8. Patients with evidence of having measured risk factors and the number of measured risk factors for thromboembolic events within 12 months before index date
- 9. Patients with evidence of having measured risk factors and the number of risk factors for malignancy within 12 months before index date
- 10. Patients with evidence of having measured risk factors and the number of risk factors for CVD within 6 months before index date

The windows for ascertainment of presence of specific events may be revised to reflect the local data flow.

Detailed methodology for summary and statistical analyses of data collected in this study will be documented in a SAP, which will be dated, filed, and maintained by the sponsor. The SAP may modify the plans outlined in the protocol; any major modifications of primary endpoint definitions or their analyses would be reflected in a protocol amendment.

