9.9. Limitations of the Research Methods

The limitations of the study are included below:

- While ritlecitinib is expected to be well-captured in outpatient dispensing streams, the Swedish national health registers have minimal capture of inpatient hospital administrations and dispensings, and partial capture of outpatient hospital administrations (i.e., medications administered in outpatient clinics located in hospitals) and dispensings. Similarly, in the SNDS, hospital admissions only capture administered medications that are expensive. Thus, most medications that are dispensed or administered primarily through hospital channels will be missed. As ritlecitinib is mainly expected to be dispensed in outpatient settings, this limitation is unlikely to result in a large proportion of missed exposed patients.
- Given the use of data sources from three distinct European countries, there will be variability in capture of indicators of adherence to the RMMs across the data sources. For example, data on laboratory tests and vaccinations are not available in Sweden and may be under recorded in Denmark and France. In France, only reimbursed vaccinations are recorded, meaning some vaccines (e.g., yellow fever vaccination) will be missed. All major variabilities in data elements across data sources will be described in the SAP.
- Other limitations, which are similar across many administrative data sources, include incomplete identification of ongoing pregnancies and pregnancies ending in a

termination (as they are identifiable only by pregnancy end date); underascertainment of lifestyle factors such as smoking status and smoking history; and challenges in identifying screening for TB and hepatitis B and C in all participating countries.

- While the study includes databases from multiple regions within the EU that have adequate data quality, results from the participating countries may not necessarily be generalizable to other countries in the EU.

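### No last event date is set apart from the last index date, so pregnancies unfinished at the data cut count as no pregnancy: unavoidable at the interim, mainly in France, and possible at the final analysis

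*Protocol*

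**What the plan says.** Section 9.1.1 sets the study period "from 15 September 2023 through 14 September 2028". Under section 9.1.2, "The date of the first dispensing or administration of ritlecitinib during the study period will be the index date", so a user may enter on the final day. Section 9.2.1 has two inclusion criteria, "Have at least one dispensing of ritlecitinib during the study period" and "Have at least 12 months of continuous history in a participating data source before the index date"; neither concerns time after the index date. Section 9.3.1 ends exposure by treatment history and gives no calendar date: "The exposure will continue until the end of a 90-day grace period following the estimated discontinuation of the index treatment". The ENCePP checklist in Annex 2 marks duration of follow-up (4.2.5) as not applicable.

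Section 6 places the end of data collection in September 2030, "Within 2 years after the end of study period", and gives data lag as the reason. It defines that milestone as the date the analytical dataset is complete, not as the last event date covered. The interim report is due in September 2028, the month in which accrual closes.

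Item 5 of section 9.7 counts "Females in whom pregnancy, as recorded in the available data sources, overlaps with ritlecitinib use"; item 2 counts laboratory tests at week 4 ± 2 weeks. Both are plain proportions, with no rule for users whose window is only partly observed. In Table 1 the French pregnancy codes are for delivery, result of delivery, abortion, termination and ectopic pregnancy. Denmark and Sweden use the whole ICD-10 O chapter. Section 9.9 lists ongoing and terminated pregnancies as incompletely identified, "as they are identifiable only by pregnancy end date".

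**The concern.** Two of the indicators need time after the index date: the week-4 tests and the overlap of pregnancy with use. If data are cut before that time has passed, the user stays in the denominator and the event cannot reach the numerator.

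The two errors run in opposite directions. A missed week-4 test makes adherence look worse, while a missed pregnancy makes it look better. The pregnancy error matters more, because no use in pregnancy is a named objective and the error is in the favourable direction. It falls mainly on France, by far the largest of the three populations (about 67 million, against 5.8 million in Denmark and 10.64 million in Sweden), and it weighs most on the interim, the first result to be reported.

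**Working it through.** The protocol gives no figure for run-out or for incomplete windows, so there is none to reproduce on this point. Its study-size figure does reproduce: 0.5 × 0.5 × 1.96² / 0.05² = 384.2, rounded up to 385. It serves below for scale only.

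**Inputs from the protocol**
- Study period, 15 September 2023 to 14 September 2028: 1,827 days.
- Week-4 window: days 14 to 42 after the index date.
- Interim report due September 2028; dataset complete September 2030.

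**Assumptions, not in the protocol**
- Term pregnancy of 280 days, conceived on treatment and found only by its end.
- Use uniform over the period, or growing linearly from zero.
- Interim cut on 14 September 2027, which gives 1,461 days.

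**Formula.** The share falling within L days of a cut, in a period of D days, is L/D for uniform use and 1 − (1 − L/D)² for linear growth.

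**Pregnancy, L = 280**
- Cut on 14 September 2028: 280/1827 = 15.3%; 1 − (1 − 0.1533)² = 28.3%.
- Interim cut: 280/1461 = 19.2%; 1 − (1 − 0.1916)² = 34.7%.

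As a cross-check for the 14 September 2028 cut, exposed time was built up from entry dates with treatment lasting 180 to 730 days. Between 16% and 34% of it then lies in the last 280 days, which is the same order.

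**Week 4, L = 42**
- Cut on 14 September 2028: 42/1827 = 2.3%; linear growth 4.5%. That is about 9 to 17 of 385 users, all with an index date after 3 August 2028.
- Interim cut: 42/1461 = 2.9%; linear growth 5.7%.
- If tests fall evenly over days 14 to 42, only 1.5–3.0% of tests are lost at the 14 September 2028 cut. At 50% adherence that is 0.5 × 1.5 = 0.75 to 0.5 × 3.0 = 1.5 percentage points, against a confidence interval half-width of 5 points at 385 patients.

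**Run-out needed after 14 September 2028**
- Week-4 tests: + 42 days = 26 October 2028.
- Pregnancy conceived by 14 September 2028: + 280 days = 21 June 2029.
- Pregnancy conceived by the end of a 90-day grace period starting that day: + 370 days = 19 September 2029.

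All three dates precede September 2030. Whether each source can deliver them depends on its data lag, which the protocol does not state.

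**The case against.** The strongest objection is that the protocol never says outcome data stop on 14 September 2028. That date bounds ritlecitinib records. The week-4 window runs from the index date, exposure has no calendar end, and the dataset is not due complete until September 2030, so a run-out could already be intended. This stands. A reader might infer that the final analysis truncates outcomes at the end of the study period, but the text supports only that the last event date is unspecified. The point does not fall with it, because the interim must be cut while accrual is open, however the final cut is read.

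Three further limits also stand. The Danish and Swedish O-chapter codes can pick up some ongoing pregnancies, so finding pregnancies by their end alone describes France. The percentages rest on an assumed cut, pregnancy length and uptake. The week-4 effect is small and does not arise in Sweden, which has no laboratory data.

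Two objections carry less weight. Section 9.9 does disclose incomplete capture of ongoing pregnancies, but as a property of the data; it does not connect this to the data cut, where part of the loss is avoidable. The SAP, not available here, may set censoring and denominator rules, and section 9.7 lets ascertainment windows be revised. However, the study period is fixed in the protocol, and section 9.6 obtains data through protocol-specific applications. An SAP rule written later cannot recover event dates that were never requested.

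**Conclusion.** The concern holds as an unspecified end of follow-up with a predictable direction of bias, not as a proven truncation. Without a rule, the French interim result for item 5 will count pregnancies unfinished at the cut as no pregnancy. The final result will do the same if outcome data end with the study period.

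The illustrative size is 15–28% of term pregnancies conceived on treatment for a cut on 14 September 2028, and 19–35% for an assumed interim cut on 14 September 2027. These are not estimates of the share of all pregnancies missed. That share is lower, because losses, terminations and pregnancies already under way at initiation end sooner. Incomplete week-4 windows affect about 2–5% of users at a 14 September 2028 cut and 3–6% at the assumed interim cut, in Denmark and France only; they would not justify a change alone. The pregnancy indicator does, and the change should be made before data are requested.

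**What to change.** In sections 9.1.1 and 9.7:

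- Keep 14 September 2028 as the last index date and leave the exposure rule of section 9.3.1 as it is.
- State a separate last event date for outcomes: at least 26 October 2028 for week-4 tests and at least late June 2029 for pregnancy ends, or about September 2029 if the 90-day grace period counts as use. Confirm for each source that its lag allows this before September 2030.
- At the interim, and at the final analysis wherever the run-out is not available, restrict item 2 to users indexed at least 42 days before the data cut, and item 5, where it relies on end-of-pregnancy codes, to exposure at least about 10 months before it. This also covers treatment that continues beyond the dates above.

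The cost is a few sentences, a later extraction end date for two data items, and slightly smaller interim denominators.
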